Official Title: ICU experience among family members of ICU patients

NCT #: NCT02940028

Document Date: May 28 2020

Protocol

Title:	ICU experience among Family Members of ICU Patients
Location of Research:	Intermountain Medical Center
Principal Investigator:	[name]
Sponsor:	Intermountain Research and Medical Foundation
Study Team:	[name] [name] [name] [name] [name] [name] [name]

Purpose of the Study:

The purpose of this study is to investigate whether an expressive writing intervention increases post-traumatic growth (PTG) in family members of patients admitted to the ICU with a serious illness and explore the association between coping phenotypes and PTG. PTG will be compared between the intervention group receiving the expressive writing intervention and the control group (non-expressive or fact-based writing). The primary outcome will be PTG at 12 weeks, with secondary outcomes of depression, anxiety and posttraumatic stress disorder (PTSD) at follow up.

Hypothesis/Research Questions:

In two hypotheses evaluated in two specific aims, we will investigate whether an expressive writing intervention increases PTG in family members of patients admitted to the ICU with a serious illness and explore the association between coping phenotypes and PTG. PTG will be compared between the intervention group receiving the expressive writing intervention and the control group (non-expressive or fact-based writing). The primary outcome will be PTG at 16 weeks, with secondary outcomes of depression, anxiety and PTSD at follow up.

Specific Aim 1: Examine the association between participating in an expressive writing intervention and development of post-traumatic growth.

Primary outcome: Post-Traumatic Growth Inventory at 4 months

Secondary outcomes: Impact of Events Scale-Revised (IESR), Hospital Anxiety and Depression Inventory (HADS) at 4 months

Hypothesis 1a: Participants in the intervention group will have higher levels of post-traumatic growth at follow-up than participants in the control group.

Hypothesis 1b: Participants in the intervention group will have lower PTSD, depression, and anxiety scores at 4 months.

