In prior work, we identified ICU family member coping phenotypes that would identify individual attributes, preferences, and vulnerabilities (personality dimensions, shared decision-making preferences, coping styles, and social support) that might be relevant to the experience of ICU surrogates²⁹. We identified three copying phenotypes including adaptive copers, maladaptive copers, and disengaged copers. Coping phenotypes differed primarily on coping styles, personality, quality of their closest social relationship, and history of anxiety and depression.²⁹ Early work suggests that individuals in certain coping phenotypes may have different approaches to surrogate decision making and different satisfaction with the shared decision making during a simulated ICU experience. They may also have different probabilities of PTG.

Research Subjects:

Inclusion Criteria:

Family members of ICU patients are eligible for the study. We will enroll **one** study participant per patient admitted to a study ICU (Shock Trauma or Respiratory ICU at Intermountain Medical Center) who meets the following inclusion criteria:

- Participant can be a family member of a patient admitted to a study ICU for >24 hours and ≥ 1 of the following:
 - mechanical ventilation via endotracheal tube for ≥ 12 hours
 - non-invasive ventilation (CPAP, BiPAP) for > 4 hours in a 24-hour period provided for acute respiratory failure in an ICU (not for obstructive sleep apnea or other stable use)
 - high flow nasal cannula or face mask O₂ with FiO₂ ≥ 0.5 for ≥ 4 hours
 - use of vasopressors for shock of any etiology for >1 hour
- The priority for enrollment is outlined in the picture below.

* A default surrogate can include (in order of preference):

- | | |
|---|-----------------------|
| 1. Spouse (unless divorced or legally separated OR if court finds spouse acted in a manner that should preclude him/her from having a priority position) | 2. Adult child |
| | 3. Parent |
| | 4. Sibling |
| | 5. Grandparent |
| | 6. Grandchild |

- Both participant and ICU patient must be adult (age ≥ 18 years of age)
- Participant must be able to read, speak, and write in English
- Participant must be enrolled within 72 hours of the patient's meeting mechanical ventilation criteria.

Participants who live with the patient will be accorded higher priority than those who do not live with the patient because they are more likely to be involved as caregivers. The preference would be for the

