Qualified study participants will be consented prior to commencing any research-related activity. These individuals will be approached in the patient's room or waiting room in the ICU or by telephone.

Methods/Procedures: Baseline Assessment

Participants will be enrolled in the study if they meet study inclusion and no exclusion criteria and signed informed consent. Participants will be administered baseline questionnaires, randomly assigned to the intervention or control condition, participate in intervention or control writing condition at 4 weeks (range 2 to 8 weeks) after enrollment, and administered follow-up questionnaires at three months after the writing intervention (\pm 2 weeks) by telephone.

Questionnaires

Participants will complete baseline questionnaires including³², PSS-4, BFI, Brief COPE, HADS and the IESR.

Table 1. Questionnaires administered at study enrollment

Instrument	Measures	Scale	Scoring
Hospital Depression and Anxiety Scale	Depression and anxiety	14 items (7 each for anxiety and depression). Items scored 0 to 3. Total scores for each scale range from 0 to 21.	Scores of 8 or higher indicate symptoms or depression or anxiety. ³³
Impact of Event Scale Revised (IES-R)	Screens for PTSD	22-item scale measuring intrusion, avoidance and hyperarousal; each item scored from 0-4	A mean score of ≥ 1.6 indicates PTSD symptoms. ^{34,35}
Perceived Stress Scale	Feelings of stress	4 items with scores that range from 0 to 4	Higher scores indicate greater stress. ^{36,37}
Brief COPE	Coping with stress	14 dimensions with 2 questions per dimension	Higher scores indicated greater use of a given coping strategy. ³⁸
Social Relationship Inventory (abbreviated)	Quality of Social Support	3 dimensions of relationship for the person closest to the respondent, helpfulness, upset, and unpredictability rated from 1 (not at all) to 6 (extremely)	Higher scores on each dimension indicate greater helpfulness, upset, and unpredictability.
Big Five Inventory	Personality dimensions: openness to new experiences, conscientiousness, extraversion, agreeableness and neuroticism.	10 items	Higher scores indicate greater degree of a specific personality characteristic. ³⁹

Random Assignment and Intervention

Random assignment to condition will be completed using random number generator. Participants will receive instructions for participating in the intervention.

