4 Month Follow-up

Four months after the writing exercise, participants will be contacted to complete an instrument battery by telephone. Follow-up measures include IES-R, HADS, PSS-4, Groningen Activities Restriction Scale (GARS) for assessing impact of the traumatic event on functional and emotional health and Posttraumatic Growth Inventory (PTGI). Following participation participants will receive gift card payment in the mail.

4 Month Follow-up			
Hospital Depression and Anxiety Scale	depression and anxiety	14 items (7 each for anxiety and depression). Items scored 0 to 3. Total	Scores of 8 or higher indicate symptoms or depression or anxiety. ³³
Impact of Event Scale Revised (IES-R)	Screens for PTSD	22-item scale measuring intrusion, avoidance and hyperarousal	A mean score of ≥ 1.6 indicates PTSD symptoms. ^{34,35}
Perceived Stress Scale	Feelings of stress	4 items with scores that range from 0 to 4	Higher scores indicate greater stress. ^{36,37}
Brief COPE	Coping with stress	14 dimensions with 2 questions per dimension	Higher scores indicated greater use of a given coping strategy. ³⁸
Post-Traumatic Growth Inventory	Positive perceptions of change following a traumatic event	21 items that use a 6 point Likert scale (0-5)	Higher Scores Indicate greater PTG
Physical Symptoms Inventory – 13 Item Version	Examines physical symptoms experienced during previous 30 days adapted to include medical utilization	13 items that use a 5 point Likert Scale (1-5)	Higher scores indicate more symptoms on more days. ^{21,24}

Groningen Activity Restriction Scale (GARS)	Assess degree of restriction experienced due to providing care in 11 categories: caring for him/herself, caring for others, eating habits, shopping for him/herself, visiting friends, working on hobbies, sports and recreation, going to work, and maintaining friendship. Developed and used in ICU populations, ⁴⁶⁻⁴⁹ shopping for him/herself, visiting friends, working on hobbies, sports and recreation, going to work, and maintaining friendship. and used in ICU populations. ⁴⁶⁻⁴⁹	11 items scored from 1 to 4	Scores range from 11 to 44 with higher scores indicating greater activity restriction.

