 - Baseline terminal illness (congestive heart failure, ESRD, liver failure, cancer)

- Study Participant information:
 - Age
 - Sex
 - Race
 - Ethnicity
 - Religion (importance, affiliation, and degree of importance)
 - Employment status
 - Number of hours weekly spent with the patient (averaged over the last month) and whether the participant lives with the patient,
 - Highest level of education.
 - Limited medical history: diagnosed depression, anxiety, sleep disorder, obesity. ^{30,31}
 - Psychiatric history of depression or anxiety
 - History of substance and alcohol abuse

The informed consent form describes the elements of PHI that will be used as a part of this study. All identifiable study information that is collected will be kept on computers owned and secured by Intermountain Healthcare. Any PHI collected for this study will be de-identified prior to disclosure to study collaborators outside of Intermountain Healthcare and only under authorization of current, valid data use agreements. The code used to de-identify these subjects will be retained by the Intermountain Healthcare Principal Investigator to allow re-identification of the subject should clarification of information be required. Identifiers of study participants will be maintained securely in order to report study results to participants, e.g., via newsletters.

We will randomize family members to receive either the PTG intervention and or non-intervention control group (control writing condition). The intervention group will participate in a brief expressive writing intervention. The control group will receive a control writing condition (fact-based writing) and complete the other study measures.

Descriptive statistics will be calculated for all demographic variables as well as all instruments (both at baseline and 4 month follow up). PTGI at 4 months (along with the secondary outcomes) will be compared between the intervention and control arms using Wilcoxon Rank Sum tests. Further, we will use linear regression to assess the relationship between expressive writing and PTGI at 4 months, adjusting for other relevant factors (i.e., participant demographics, (including age), patient demographics, illness severity of the patient, social support of the participant, caregiver burden, etc.).

Sample Size:

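### The Hypothesis 1b scores get an unadjusted Wilcoxon test although each scale has a pre-randomisation baseline; a baseline-adjusted rank test may recover power at almost no cost, by an amount the protocol cannot fix

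*Protocol*

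**What the plan says.** The analysis paragraphs at the end of the Protocol's Data Collection section fix the between-arm test: "PTGI at 4 months (along with the secondary outcomes) will be compared between the intervention and control arms using Wilcoxon Rank Sum tests". The same paragraph has one adjusted model, and it is for the primary outcome only: "we will use linear regression to assess the relationship between expressive writing and PTGI at 4 months". Baseline instrument scores appear there only under description: "Descriptive statistics will be calculated for all demographic variables as well as all instruments (both at baseline and 4 month follow up".

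Hypothesis 1b, under Specific Aim 1, reads: "Participants in the intervention group will have lower PTSD, depression, and anxiety scores at 4 months". The scales are the IES-R and the two HADS subscales.

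Methods/Procedures puts the baseline battery ahead of allocation: "Participants will be administered baseline questionnaires, randomly assigned to the intervention or control condition". The Questionnaires section lists "PSS-4, BFI, Brief COPE, HADS and the IESR" in that battery. The 4 Month Follow-up section repeats them: "Follow-up measures include IES-R, HADS, PSS-4". PTGI is collected at follow-up only.

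**The concern.** Each Hypothesis 1b scale is measured on the same participants before randomisation and again at follow-up, yet the named test ignores the first measurement. When baseline and follow-up scores are correlated, adjusting for baseline removes outcome variance that has nothing to do with treatment, and so raises power with no extra data.

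This could matter because the Sample Size section derives its 102 from PTGI, so nothing in the protocol secures power for Hypothesis 1b. The choice should also be made in advance: an adjustment added after the results are known would look selective.

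**Working it through.** **1. The protocol's own figure.** Sample Size assumes PTGI means of 45 and 56; the superscripts 18 and 21 are read as SDs. Pooled SD = √((18² + 21²)/2) = 19.56, so d = 11/19.56 = 0.562. With two-sided alpha 0.05 and 80% power (neither sidedness nor power is stated), the normal formula gives 49.6, so 50 per arm. The exact t-test gives 51 per arm, 102 in total, which reproduces the stated number. Dividing the normal-formula size by the Wilcoxon efficiency 3/π gives 104. The 102 therefore belongs to PTGI, and 51 per arm is the evaluable size used below.

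**2. Analytic gain.** Relative variance of an adjusted to an unadjusted comparison ≈ (1 − r²)(1 + 1/(N − 4)), with N = 102:

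- r = 0: 1.010
- r = 0.2: 0.96 × 1.0102 = 0.970
- r = 0.3: 0.91 × 1.0102 = 0.919
- r = 0.5: 0.75 × 1.0102 = 0.758

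Break-even is at r² = 1/99, so r ≈ 0.1. Ignoring the lost degree of freedom, 102 adjusted participants are worth 102/0.91 = 112 unadjusted at r = 0.3 and 102/0.75 = 136 at r = 0.5.

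**3. Simulated power, uniform shift.** Assumptions not in the protocol: a 0.4 SD shift on a latent normal scale, 51 per arm, two-sided 0.05, and r as the latent correlation. There were 20,000 trials per cell (Monte Carlo SE about 0.35 points). HADS-like scores are round(exp(1.6 + 0.7z) − 1), clipped to 0–21. Quade's test ranks outcome and baseline over both arms, regresses the first ranks on the second ignoring arm, and compares the residuals between arms.

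| r | HADS-like: Wilcoxon / Quade | Normal: Wilcoxon / Quade | Change, points |
|---|---|---|---|
| 0 | 48.7 / 48.5% | 49.9 / 49.8% | −0.2; −0.1 |
| 0.2 | 49.0 / 50.0% | 49.3 / 50.4% | +1.0; +1.1 |
| 0.3 | 48.8 / 51.8% | 49.9 / 53.0% | +3.0; +3.1 |
| 0.5 | 48.9 / 59.1% | 49.2 / 59.5% | +10.2; +10.3 |
| 0.6 | 48.8 / 65.2% | 49.2 / 66.3% | +16.4; +17.1 |

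Log-normal scores behave alike. For HADS-like scores at r = 0.5, power goes from 30.7% to 37.4% with a 0.3 SD effect and from 68.6% to 78.8% with 0.5 SD. Type I error stayed between 4.6% and 5.4% for the Wilcoxon and Quade tests.

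**4. Effect only in participants above the median baseline**, with the average shift still 0.4 SD. HADS-like, Wilcoxon / Quade: r = 0.2, 47.9 / 47.9%; r = 0.3, 49.7 / 50.1%; r = 0.5, 53.0 / 56.8%. Normal: r = 0.3, 50.1 / 50.4%; r = 0.5, 52.8 / 56.7%. At r = 0.6 the gain is about 8 points. The largest loss was about 0.4 points. A uniform shift with a floor at follow-up and a ceiling at baseline falls between the two cases: about +2 at r = 0.3 and +6 at 0.5.

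**5. Missing baselines**, 10% at random, HADS-like, uniform 0.4 SD shift:

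| r | Wilcoxon | Quade, complete cases | Quade, pooled-median imputed |
|---|---|---|---|
| 0 | 49.2% | 44.5% | 49.1% |
| 0.3 | 49.7% | 48.2% | 52.5% |
| 0.5 | 48.8% | 54.3% | 57.6% |

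Dropping these participants costs about 5 points at r = 0 and removes the gain at r = 0.3. Imputation avoids this.

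**6. Why a rank test.** ANCOVA on raw scores with HC3 standard errors can do worse than Wilcoxon when scores are skewed. At r = 0.2 its power is 40% against 49% (log-normal) and 44% against 49% (HADS-like).

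**The case against.** The strongest reply is that this is no defect. The Wilcoxon test is valid and unbiased under randomisation, and covariate adjustment of secondary outcomes is commonly left to a statistical analysis plan, which is not at hand and may already provide it. That stands as far as it goes, and limits the point to efficiency. But the protocol is not silent here: it names an unadjusted test, and that named choice is what is questioned.

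Second, r is unknown, and the design gives reasons for a low value. The Inclusion Criteria say "Participant must be enrolled within 72 hours" of the qualifying event, the IES-R in Appendix 1 asks about the past 7 days, and follow-up comes months later. This stands: at r of 0.2 or less the gain is about 1 point or none.

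Third, a reader might infer that adjustment pays whenever r reaches about 0.3. The documents do not support such a threshold. It holds for a shift that is the same at every baseline level. Participants with few symptoms have little room to improve, and if only those with high baselines benefit, the gain at r = 0.3 nearly vanishes.

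Fourth, the remedy adds specification for three secondary outcomes. That is fair, and it is why the mean-difference interval is left optional.

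**Conclusion.** The point holds as an optional improvement in efficiency. The named test leaves unused a baseline already collected for each Hypothesis 1b score. Under the assumptions shown (51 per arm, 0.4 SD average shift), the gain runs from nothing at r = 0 to about 10 points at r = 0.5 and 16 at r = 0.6 for a uniform shift. It is about 4 and 8 points at those two correlations if the effect lies only in participants with above-median baselines. With baselines complete or imputed, the loss never exceeded about half a point, so the trade-off favours adjustment even though r is unknown.

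A reader might go further and conclude that the secondary results would be biased or the trial undersized. Neither follows. Randomisation protects the Wilcoxon test, PTGI has no baseline to adjust for, and the 102 and 130 are unchanged. Nor does adjustment make Hypothesis 1b well powered: at r = 0.5 with a uniform 0.4 SD shift, power is still only about 59–60%, so a null result would remain inconclusive.

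**What to change.** In the analysis paragraphs of Data Collection, name a Quade rank ANCOVA on the same scale's baseline score, two-sided 0.05, as the between-arm test for IES-R, HADS-anxiety and HADS-depression. State that:

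- every participant with a 4-month score is included;
- a missing baseline is replaced by the median of both arms combined, without reference to arm;
- a response brought in under Copying Data Already Collected counts as baseline only if dated before randomisation, and is otherwise treated as missing and imputed;
- the unadjusted Wilcoxon test is kept as a sensitivity analysis.

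A baseline-adjusted mean difference with an HC3 95% interval may be added as descriptive only. If it is, say that it can disagree with the rank test: across r = 0 to 0.6, Quade was significant while this interval included zero in 10–13% of HADS-like trials and 15–20% of log-normal ones.

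The cost is a change of wording, a little programming, about one degree of freedom per scale, a missing-baseline rule and a date check. No new data are needed. The return may be near zero if r is low or the effect is concentrated in those with high baseline scores.

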Specific Aim 2: Explore whether individual coping phenotypes predict PTG. Predictors for consideration include acute perceived stress (Perceived Stress Scale-4 [PSS-4], personality characteristics (Big Five Inventory [BFI]) coping ability (Brief COPE), social relationship quality (Social Relationship Inventory (SRI abbreviated), measures of disability in activities of daily living and instrumental activities of daily living caregiver burden (Groningen Activity Restriction [GARS] Scale), patient age and severity of illness (APACHE score).

Hypothesis 2a: ICU families coping phenotypes (stress, personality characteristics, and coping) will be associated with PTG.

Hypothesis 2b: Other variables related to the ICU (APACHE IV score, age, sex, ethnicity, whether the patient dies before follow-up) and post-ICU (care giver burden) experience will be associated with PTG at 3 mos.

Background and Significance:

Post-ICU psychological distress is common and important

The intensive care unit (ICU) is a stressful and challenging place for patients and their families, who must navigate illness and its associated discomforts as well as complex decision making in an environment characterized by tremendous uncertainty¹⁻³. Negative emotions including stress, fear, anger, and fatigue are extremely common during an ICU admission^{4,5}. Many family members experience anxiety, depression, and posttraumatic stress disorder (PTSD) during and after the ICU experience that persists years after their loved one is discharged from the ICU^{3,6-8}.

During an ICU stay, it is common for patients to be too ill to participate in decision making in the ICU⁹ – and medical decision making will generally be made by the family members designated surrogate decision makers⁷. Surrogate medical decision making may be intense and stressful and may contribute to development of anxiety, depression and posttraumatic stress disorder (PTSD) in family members³.

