Post traumatic growth takes time to emerge, with most positive changes occurring within 2 months after the trauma¹⁸ while the level of PTG remains stable 3 to 8 years following the trauma^{19,20}.

Potential Benefits of Expressive Writing

Although PTG is a naturally occurring process, deliberate interventions can increase its likelihood. Some interventions are time-consuming and expensive – such as cognitive behavioral therapy. But, in some contexts, interventions centered on a specific type of journaling known as “expressive writing” have increased PTG. Semi-structured expressive writing was developed by [name]. as a structured technique for recording deep thoughts and feelings about a traumatic event in a structured setting²¹. Expressive writing facilitates coping with trauma by helping people process – emotionally and cognitively – a traumatic event. Participating in expressive writing – commonly three 20-minute sessions on three consecutive days – includes writing about emotions and thoughts associated with the traumatic event. Variations include providing participants with a journal and asking them to complete the writing at set times at home²² or using an internet-based journal²³. In many studies expressive writing interventions are associated with improved outcomes including fewer reports of physical symptoms, a reduction in PTSD and greater PTG²²⁻²⁴. In addition, expressive writing is associated with reduced healthcare utilization, fewer physical symptoms, and fewer PTSD symptoms on follow-up^{21,22,25}.

Family members and patients enter the ICU with unique characteristics that may affect their risk for psychological distress²⁶. In other trauma-exposed populations, individual attributes have been associated with development of PTSD^{26,27}. Personalizing the experience of family members by offering post-ICU support strategies, such as writing interventions, may decrease psychological distress and improve positive outcomes and PTG^{11,28}.

[figure not shown]

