Groningen Activity Restriction Scale (GARS)	Assess degree of restriction experienced due to providing care in 11 categories: caring for him/herself, caring for others, eating habits, sleeping habits, doing household chores, going	11 items scored from 1 to 4	Scores range from 11 to 44 with higher scores indicating greater activity restriction.
Essay Evaluation Measure	Perception that essay was personal, meaningful and revealing of their emotions	Each item Likert 0-6 total range 0-18	Higher scores indicate that participants found the essay personal and meaningful and revealing of their emotions (0-18) ⁵⁰
Evaluation of essays not done with participant			

Informed Consent:

Study-designated Intermountain Healthcare employees (either the research coordinator(s) or the study investigator(s)) will obtain informed consent from the study participant. The study staff member obtaining consent will provide the participant with the current IRB-approved Informed Consent Form and will be available to answer any questions the participant may have. Individuals approached for consent will be given as much time as they require to consider enrollment in the study.

The ICU patient will not be approached or questioned. They are indirectly involved, as the study participant is defined by their relationship to the patient. Minimal information will be obtained about the patient from the medical record to allow assessment of the effects of acute severity of illness or length of stay. The ICU patient will not be consented as they are not the subject of the study and minimal information is collected regarding these individuals. We will ask for a waiver of informed consent to gather this data.

Waiver of Informed Consent

The ICU patients are not directly involved and will not be approached or questioned. Minimal information will be obtained about the patients. The ICU patients will not be consented as they are not the subject of the study and minimal information is collected regarding these individuals. We will ask for a waiver of informed consent to gather this data. We feel it is not necessary or appropriate to obtain consent from the ICU patients for these reasons.

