Appendix 4.

Groningen Activity Restriction Scale (GARS)

The following questions refer to daily activities which should be performed frequently. In each question it is asked whether you *are able to perform* the activity at this moment. It is not intended to assess whether you are actually performing the activities, but if you can do them if necessary.

Response categories for each item

1. Yes, I can do it fully independently without any difficulty
2. Yes, I can do it fully independently but with some difficulty
3. Yes, I can do it fully independently but with great difficulty
4. No, I cannot do it fully independently, I can only do it with someone’s help

GARS items

1. Can you, fully independently, dress yourself?
2. Can you, fully independently, get in and out of bed?
3. Can you, fully independently, stand up from sitting in a chair?
4. Can you, fully independently, wash your face and hands?
5. Can you, fully independently, wash and dry your whole body?
6. Can you, fully independently, get on and off the toilet?
7. Can you, fully independently, feed yourself?
8. Can you, fully independently, get around in the house (if necessary with a cane or walker)?
9. Can you, fully independently, go up and down the stairs?
10. Can you, fully independently, walk outdoors (if necessary with a cane or walker)?
11. Can you, fully independently, take care of your feet and toenails?
12. Can you, fully independently, prepare breakfast or lunch?
13. Can you, fully independently, prepare dinner?
14. Can you, fully independently, do “light” household activities (for example, dusting and tidying up)?
15. Can you, fully independently, do “heavy” household activities (for example mopping, cleaning the windows, and vacuuming)?
16. Can you, fully independently, wash and iron your clothes?
17. Can you, fully independently, make the beds?
18. Can you, fully independently, do the shopping?

Activity Restriction Scale (ARS)

“Please tell me how much you have restricted your activities in each of the following areas due to the care you are providing to your loved one:	
1. Care of yourself?	 1 Not restricted at all  2 Slightly restricted  3 Moderately restricted  4 Greatly restricted

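### The regression of 4-month PTGI on writing arm adjusts for caregiver burden, which is measured only at follow-up, so the arm coefficient is biased if writing changes reported burden

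*Protocol*

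**What the plan says.** The last paragraph of Data Collection compares 4-month PTGI between arms with a Wilcoxon rank sum test. It then adds a linear regression of PTGI on expressive writing, adjusted for participant and patient demographics and for "illness severity of the patient, social support of the participant, caregiver burden, etc".

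Specific Aim 2 identifies the burden measure: "instrumental activities of daily living caregiver burden (Groningen Activity Restriction [GARS] Scale". Hypothesis 2b classes it as a variable arising after the ICU and expects it to be related to growth: "post-ICU (care giver burden) experience will be associated with PTG at 3 mos".

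The enrolment questionnaires are listed as "PSS-4, BFI, Brief COPE, HADS and the IESR". Table 1 adds the abbreviated Social Relationship Inventory. Neither place contains a burden scale. The 4 Month Follow-up section is where the scale appears: "Follow-up measures include IES-R, HADS, PSS-4, Groningen Activities Restriction Scale (GARS) for assessing impact of the traumatic event on functional and emotional health". PTGI is collected in the same telephone contact.

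The instrument itself is described in two ways. The follow-up table gives the GARS 11 items on restrictions due to providing care: "Scores range from 11 to 44 with higher scores indicating greater activity restriction". Appendix 4 prints under that name an 18-item scale of the respondent's own physical abilities, ending with "Can you, fully independently, do the shopping". It then prints a separate 11-item Activity Restriction Scale (ARS).

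**The concern.** An arm coefficient in a randomised trial estimates the effect of assignment when the covariates beside it cannot have been altered by assignment. Demographics, severity at admission and social support at enrolment meet that condition. Burden recorded months after the writing does not.

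Bias needs two things: burden must be related to PTGI within arm, and writing must change reported burden. Hypothesis 2b asserts the first. The second is not stated, but the protocol gives reason not to assume it away. It reports that "expressive writing is associated with reduced healthcare utilization, fewer physical symptoms, and fewer PTSD symptoms on follow-up", Hypothesis 1b predicts lower distress in the writing arm, and the scale is said to reflect functional and emotional health.

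This regression is the only adjusted estimate of the arm effect that the protocol describes. If it departed from the unadjusted result, a reader could not tell ordinary covariate adjustment from bias introduced by the burden term. The relation need not be causal: an unmeasured cause shared by burden and growth is enough.

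**Working it through.** **Order of events** (Methods/Procedures; 4 Month Follow-up): baseline questionnaires, randomisation, writing, follow-up call. The text puts that call three months after writing in one place and four in another. Under either, burden is measured after randomisation and writing.

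**Planning inputs** (Sample Size): means 45 and 56, with the raised 18 and 21 read as SDs; 102 evaluable, 51 per arm.
- Difference: 56 − 45 = 11.
- Pooled SD: √((18² + 21²)/2) = √382.5 = 19.56.

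**The plan's own figure.** Power and sidedness are not stated. Assuming 80% and two-sided 0.05, the two-means formula gives n per arm = 2 × (1.960 + 0.842)² × 382.5/11² ≈ 49.6, so 50 per arm and 100 in all, close to the stated 102. Simulated Wilcoxon power at 51 per arm is 78.8%. The point below does not depend on this figure.

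**Bias formula.** Let δ be the shift in burden caused by writing, in SD units, and γ the within-arm slope of PTGI per SD of burden, whatever its source. In the linear model:

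adjusted coefficient = 11 − δ × γ, so bias = −δγ.

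The documents give neither δ nor γ, so both are assumed. Slopes of 4 and 6 points per SD correspond to within-arm correlations of 4/19.56 = 0.20 and 6/19.56 = 0.31.

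| δ (SD) | γ = −6 | γ = −4 | γ = +4 | γ = +6 |
|---|---|---|---|---|
| 0 | 11.0 | 11.0 | 11.0 | 11.0 |
| −0.2 | 9.8 | 10.2 | 11.8 | 12.2 |
| −0.3 | 9.2 | 9.8 | 12.2 | 12.8 |

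Positive δ mirrors the table. A steeper slope of 10 (correlation 10/19.56 = 0.51) with a 0.3 SD shift gives a bias of 3 points.

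**Simulation check.** In a linear model with 1,000,000 records and a true difference of 11:
- δ = −0.3, γ = −4: adjusted coefficient 9.79 (formula 9.8).
- δ = −0.3, burden with no effect of its own but a shared unmeasured cause giving a net slope of +4: 12.19 (formula 12.2).
- δ = −0.3, both mechanisms together so that the net slope is zero: 10.99, no bias.
- δ = 0: about 11 in every case.

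**Could the trial show that δ is zero?** At 51 per arm, the 95% half-width for the arm difference in burden is 1.984 × √(2/51) = 0.39 SD. Two-sided power is 17% for a 0.2 SD shift and 32% for 0.3 SD. A non-significant burden comparison would not be reassuring.

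**Which score would enter the model?** Eleven items scored 1 to 4 give 11 to 44. Eighteen items scored 1 to 4 give 18 to 72. The range in the follow-up table therefore fits the ARS in Appendix 4, not the scale printed there as the GARS.

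**The case against.** The strongest reply is that nothing shows that writing moves caregiver burden. The scale is described as reflecting the impact of the traumatic event, not of the writing. The cited benefits are symptoms and healthcare use. The ARS items ask about restrictions due to the care being given, which depend largely on the patient's needs. Both arms write about the same ICU stay for three 20-minute sessions. A shift near zero is quite possible, and then there is no bias. This stands, and it is why the point is conditional.

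The assumed bias is also modest against sampling error. The standard error of the arm difference is 19.56 × √(2/51) = 3.87, a 95% half-width of about 7.7 points, so 0.8 to 1.8 points is roughly 0.2 to 0.5 of a standard error. This stands too. Unlike sampling error, however, the bias does not shrink with more participants and is not reflected in the confidence interval.

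The Wilcoxon comparison, on which the sample size rests, is untouched, and the covariate list is open-ended. True, but burden is named in it, so a later analysis plan could leave it out only by departing from the protocol.

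Finally, a baseline burden measure might exist. The reference list includes another caregiver burden interview (references 43 to 45) that no visible text cites, and answers may be copied from a companion study. Neither shows a burden scale at enrolment: Aim 2 names the GARS, the list of appendices contains no other burden scale, and the copying provision does not name one.

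**Conclusion.** The concern holds. A named covariate in the arm-effect regression is measured after randomisation and writing, together with the outcome. If writing leaves reported burden unchanged, the coefficient is unbiased. For shifts of 0.2 to 0.3 SD and slopes of 4 to 6 points per SD, the estimate would lie between 9.2 and 12.8 instead of 11; the sign is unknown in advance, and 3 points is reached only with a strong correlation. These sizes rest on assumed inputs and a linear model. The trial is too small to establish that the shift is absent. The damage is confined to the adjusted estimate, so this should be corrected but does not undermine the main comparison. The mismatch between the follow-up table and Appendix 4 is a separate contradiction that leaves the burden score undefined for any use.

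**What to change.** In the analysis paragraph, remove caregiver burden, and any other variable first measured at follow-up, from the regression that estimates the writing effect. Limit adjustment to enrolment variables already collected: participant and patient demographics, admission APACHE score and baseline social support. Name one APACHE version, since Hypothesis 2b says IV and Data Collection says II.

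Keep follow-up burden as a predictor for Hypothesis 2b. If its role between writing and growth is of interest, label that a mediation analysis.

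Reconcile Specific Aim 2 and the follow-up table with Appendix 4: name which printed scale is the burden measure (the 11 to 44 range matches the ARS) and say whether the 18-item GARS is also administered.

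The cost is one sentence in the analysis section and a corrected instrument name. No additional data are needed and the sample size does not change.
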